#### 6.3.3 Safety Analysis

As this study presents no more than minimal risk to study participants, a safety analysis will not be performed. If any safety risks are realized, see section 8.2 for adverse event reporting.

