#### 7 STUDY INTERVENTION

#### 7.1 Description

Intervention: Subjects will be randomized within the WTH platform to 1 of 3 financial incentive groups:

- 1) Quitline Incentive: the payment structure emphasizes engaging with the quitline, with an additional smaller payment for smoking cessation. Each adolescent can receive \$15 payments for enrolling in the quitline, for maintaining involvement in the quitline program (\$15 per call for up to 5 calls), and, for those reporting abstinence, \$20 for submitting the cotinine swab and \$25 for confirmed quitting (negative cotinine swab);
- 2) Smoking Cessation Incentive: the payment structure emphasizes quitting regardless of engagement with the quitline (though the quitline will be presented as a helpful tool). Each adolescent will receive \$15 for enrolling in the quitline and, for those reporting abstinence, \$20 for submitting the cotinine swab and \$100 for confirmed quitting (negative cotinine swab); and
- 3) No financial incentive.

The WTH platform has secure financial tracking and processing systems to manage participant payments, including the ability to track earnings and pay participants via a nonintegrated payment system (ClinCard) ideally suited for adolescent subjects. ClinCards are reloadable, prepaid cards managed by Greenphire. Subjects will be able to access the payments during the study duration. Payments are based off the following:

- Enrolling in the Quitline Program, defined as the subject connecting with a Quitline counselor, providing basic information about smoking history, and discussing program details (see "Quitline Delivered Treatment" section below). To receive this payment, subjects must enroll in the Quitline within 2 weeks of start of the study;
- Maintaining involvement in the program, defined as the subject engaging in 5 proactive counseling calls with the Quitline counselors. Calls are scheduled every 1-2 weeks, depending upon the needs of the subject, and the Quitline counselor reaches out to the subject to initiate the call. Subjects eligible to receive payments for quitline calls must complete each call within a 2-week designated window;
- **Submitting the Cotinine Swab,** defined as, for those subjects who self-report quitting smoking (defined as no tobacco use in past 30 days) at the 10-week follow-up call, successfully completing the cotinine-specimen within 2 weeks of the call.

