- **Quit Confirmed**, defined as a salivary cotinine measurement concentration of <30 ng per milliliter.

Subject engagement with the Quitline will be reported back to the WTH platform in real time using secure, password-protected methods. This allows subjects, through their interactions with the WTH platform, to see regular progress reports of their payments. See Table 1 for payment structure.

All subjects across the 3 groups, regardless of their level of engagement with the Quitline, will be contacted by the study team at 10 weeks after study enrollment to assess their smoking status. For those reporting quitting smoking, they will be asked to complete the salivary cotinine measurement.

Table 1: Payment Structure									
	Connect to Way to Health	Quitline Enrollment	Quitline Counseling Calls			Submit Cotinine Swab*	Quit Confirmed ^		
Incentive, Quitline	\$15	\$15	\$15	\$15	\$15	\$15	\$15	\$20	\$25
Incentive, Smoking Cessation	\$15	\$15	0	0	0	0	0	\$20	\$100
No Incentive	\$15	0	0	0	0	0	0	\$20	0

\*For subjects that report quitting smoking (defined as no tobacco use in past 30 days) at the 10-week followup call. All subjects will receive \$20 for submitting the salivary cotinine swab, regardless of the result. ^Payment received for negative result, meaning cotinine level <30 ng per milliliter

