#### 8 SAFETY MANAGEMENT

#### 8.1 Clinical Adverse Events

Clinical adverse events (AEs) will be monitored throughout the study.

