### 8.2 Adverse Event Reporting

Since the study procedures are not greater than minimal risk, SAEs are not expected. If any unanticipated problems related to the research involving risks to subjects or others happen during the course of this study (including SAEs) they will be reported to the IRB in accordance with CHOP IRB SOP 408: Unanticipated Problems Involving Risks to Subjects. AEs that are not serious but that are notable and could involve risks to subjects will be summarized in narrative or other format and submitted to the IRB at the time of continuing review.

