# 9.4 Regulatory and Ethical Considerations

## 9.4.1 Data and Safety Monitoring Plan

The study PI will monitor and review the study progress, the accuracy and security of the emerging data, and will maintain oversight over data integrity. Identifying information collected for study or recruitment purposes will be stored securely. No PHI will be retained for future research, as it will be destroyed upon closure of the study protocol. No other PHI identifiers will be collected at any time, and no other PHI identifiers will be stored.

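### Adverse events are to be monitored throughout, but no procedure is described for finding them and no count by arm is planned, so a low or zero count would say little about the minimal-risk claim

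*Combined protocol and SAP*

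**What the plan says.** Section 8.1 consists of one commitment: "Clinical adverse events (AEs) will be monitored throughout the study". It gives no method, question, timing or responsible role. Section 6.3.3 states that, because risk is no more than minimal, "a safety analysis will not be performed". It then adds: "If any safety risks are realized, see section 8.2 for adverse event reporting".

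Section 8.2 sets out what happens to events once they are known. For unanticipated problems, including serious events, "they will be reported to the IRB in accordance with CHOP IRB SOP 408". Notable non-serious events "will be summarized in narrative or other format and submitted to the IRB at the time of continuing review".

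The other relevant places are these:

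- Section 5.3 (Safety Evaluation) states that risk is minimal and lists no measurement.
- Section 9.4.1, titled as the data and safety monitoring plan, says "The study PI will monitor and review the study progress, the accuracy and security of the emerging data". It does not mention events.
- Section 7.1 says that all subjects "will be contacted by the study team at 10 weeks after study enrollment to assess their smoking status". Section 3.1.3 describes the same contact as an inquiry about cessation. For the counselling calls before then, "the Quitline counselor reaches out to the subject to initiate the call".
- Section 9.2 says that WTH and Quitline interactions are reported back to the study team to check benchmarks and resolve problems.
- Section 9.4.2 names breach of confidentiality as the main risk. Section 9.2 mentions inadvertent disclosure to a parent or guardian as one form of it.

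**The concern.** The promise in section 8.1 has no procedure behind it. The only study-team contact scheduled for every subject after randomisation has smoking status as its stated content. The calls before it are made by Quitline counsellors, and adverse events are not among the stated purposes of what is reported back.

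This matters most for the harm that the protocol itself puts first. If a parent learns of an adolescent's tobacco use through the study, the adolescent may be the only person in a position to report it. Subjects aged 14 to 17 consent for themselves (section 9.6.1), so this form of the risk is relevant to the population. The privacy check at the start of study phone calls (section 9.2) is there to prevent a breach; it does not record whether one has occurred.

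The trial is a pilot for a larger study (section 6.4) and rests on a minimal-risk claim. Passive capture cannot tell the absence of events from the absence of reports, and without a denominator and a breakdown by arm the few events that surface cannot be put to much use in planning the next trial.

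**Working it through.** **Inputs from the documents.** Section 6.4 gives 20 per group in 3 groups: 3 × 20 = 60, which agrees with the stated total. Section 3.3.2 expects about 70 enrolled for 60 evaluable, an implied loss of 1 − 60/70 = 14.3%. The documents give no adverse event rate, no breach rate and no safety sample size, so there is no safety figure to reproduce.

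**Assumptions.** Let p be the true proportion of subjects with an event and s the share of those events that reach the study team. Neither is in the documents. I take p = 2%, 5% and 10%, and s = 1 (everyone asked and reporting), 0.5, 0.25 and 0.10.

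**Chance of recording no event among 60.** The formula is (1 − p·s)^60. For p = 5%, where 60 × 0.05 = 3 events are expected:

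- s = 1: 0.95^60 = 4.6%
- s = 0.5: 0.975^60 = 21.9%
- s = 0.25: 0.9875^60 = 47.0%
- s = 0.10: 0.995^60 = 74.0%

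All three rates together:

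| True rate p | s = 1 | s = 0.5 | s = 0.25 | s = 0.10 |
|---|---|---|---|---|
| 2% | 29.8% | 54.7% | 74.0% | 88.7% |
| 5% | 4.6% | 21.9% | 47.0% | 74.0% |
| 10% | 0.2% | 4.6% | 21.9% | 54.7% |

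**What a zero count would rule out.** With zero recorded among n, the exact one-sided 95% upper limit for the recorded rate is 1 − 0.05^(1/n). For n = 60 this is 1 − 0.05^(1/60) = 4.87%. Dividing by s gives the limit for the true rate:

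- s = 1: 4.9%
- s = 0.5: 0.0487/0.5 = 9.7%
- s = 0.25: 0.0487/0.25 = 19.5%
- s = 0.10: 0.0487/0.10 = 48.7%

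For one arm of 20 with everyone asked, the limit is 1 − 0.05^(1/20) = 13.9%.

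**Timing of a week-10 question.** Under section 7.1 the swab may be completed up to 2 weeks after the week-10 call, and under section 9.2 it may be mailed to the home. From Table 1, the most that can be paid after the call is $20 + $25 = $45 in the Quitline arm, $20 + $100 = $120 in the cessation arm and $20 in the control arm. A question asked only at week 10 would miss the mailing and these payments, and the payments it missed could differ by arm.

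**The case against.** The strongest defence is that this is a reasoned and disclosed choice. The study refers adolescents to a free service they can already use, its stated goals are feasibility and effect size, and 20 per arm cannot usefully compare rare events. That stands as a reason to omit formal safety testing. It does not supply the missing ascertainment or explain why no descriptive count is planned.

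A reader might infer that the trial is built to report no harms. The documents do not support this. Section 6.3.3 points to section 8.2, which takes known events to the IRB, and nowhere is a no-harms statement planned. In the 5% illustration, the chance of recording at least one event is still 26% to 78% when 10% to 50% of events surface. A reader might also infer that nobody asks about events. Call scripts are not in the documents, so the most that can be said is that no contact is described as asking.

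Nor would every breach be known only to the subject. Identifiers pass between several data holders (section 9.2), a leak there could be noticed by one of them, and the investigator's oversight of data security bears on it. The point is strongest for disclosure at home.

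Finally, one might argue that risk differs by arm because maximum payments are $150, $150 and $35. That is weak. These are maxima, every arm receives $15 for connecting to WTH, every arm is offered the same counselling, and nothing in the documents links payment size to disclosure. The case for counts by arm is ordinary trial reporting and needs no such link.

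**Conclusion.** The concern holds as a gap in ascertainment and description. Sections 5.3, 6.3.3, 8.1 and 9.4.1 together promise monitoring without a described means of finding events, a reviewer of them, a denominator or a count by arm. Section 8.2 handles events once known but does not look for them. A low or zero count of the protocol's own main risk would therefore be weak evidence for the minimal-risk claim.

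The size of the effect depends on two assumed quantities. Across the assumed rates of 2% to 10%, passive capture always makes a zero count more likely than asking everyone does, but never certain. At the 2% rate, asking everyone still leaves a 30% chance of zero. The documents do not support the stronger conclusion that harms are hidden by design or that a clean record is guaranteed. This is an inexpensive improvement worth making and does not call the trial's main comparisons into question.

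**What to change.** 1. At the existing week-10 call, ask all three arms the same two fixed questions: whether anyone learned of the subject's tobacco use or participation because of the study, and whether anything else unwanted happened. The privacy check in section 9.2 already opens such calls.
2. Repeat both questions at the existing swab contact for those who provide a swab. State that payments made after the swab remain unasked.
3. In section 6.3.3, replace the no-analysis statement with descriptive counts by randomised arm, the number asked and exact confidence intervals, without formal testing. Report week-10 answers separately from swab-contact answers, because only subjects who report abstinence have the second contact. Giving the number asked also makes losses visible.
4. Add event review to the investigator's duties in section 9.4.1, and name the two contacts in section 8.1, so that the sections agree.

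The cost is about a minute per call, one descriptive table, and a few more minor events to summarise under section 8.2. The gain is limited: zero events in an arm of 20 still leaves a one-sided 95% upper bound of about 14%. Once the week-10 calls have passed without the questions, the answers can no longer be collected prospectively.

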#### 6.4 Sample Size and Power

The goals of this pilot project are feasibility and estimation of effect size and, therefore, no formal sample size calculations are performed. We anticipate 20 participants per group (60 total) will provide sufficient data to determine effect sizes to power a future larger grant.

#### 7 STUDY INTERVENTION

#### 7.1 Description

Intervention: Subjects will be randomized within the WTH platform to 1 of 3 financial incentive groups:

- 1) Quitline Incentive: the payment structure emphasizes engaging with the quitline, with an additional smaller payment for smoking cessation. Each adolescent can receive \$15 payments for enrolling in the quitline, for maintaining involvement in the quitline program (\$15 per call for up to 5 calls), and, for those reporting abstinence, \$20 for submitting the cotinine swab and \$25 for confirmed quitting (negative cotinine swab);
- 2) Smoking Cessation Incentive: the payment structure emphasizes quitting regardless of engagement with the quitline (though the quitline will be presented as a helpful tool). Each adolescent will receive \$15 for enrolling in the quitline and, for those reporting abstinence, \$20 for submitting the cotinine swab and \$100 for confirmed quitting (negative cotinine swab); and
- 3) No financial incentive.

The WTH platform has secure financial tracking and processing systems to manage participant payments, including the ability to track earnings and pay participants via a nonintegrated payment system (ClinCard) ideally suited for adolescent subjects. ClinCards are reloadable, prepaid cards managed by Greenphire. Subjects will be able to access the payments during the study duration. Payments are based off the following:

- Enrolling in the Quitline Program, defined as the subject connecting with a Quitline counselor, providing basic information about smoking history, and discussing program details (see "Quitline Delivered Treatment" section below). To receive this payment, subjects must enroll in the Quitline within 2 weeks of start of the study;
- Maintaining involvement in the program, defined as the subject engaging in 5 proactive counseling calls with the Quitline counselors. Calls are scheduled every 1-2 weeks, depending upon the needs of the subject, and the Quitline counselor reaches out to the subject to initiate the call. Subjects eligible to receive payments for quitline calls must complete each call within a 2-week designated window;
- **Submitting the Cotinine Swab,** defined as, for those subjects who self-report quitting smoking (defined as no tobacco use in past 30 days) at the 10-week follow-up call, successfully completing the cotinine-specimen within 2 weeks of the call.
- **Quit Confirmed**, defined as a salivary cotinine measurement concentration of <30 ng per milliliter.

Subject engagement with the Quitline will be reported back to the WTH platform in real time using secure, password-protected methods. This allows subjects, through their interactions with the WTH platform, to see regular progress reports of their payments. See Table 1 for payment structure.

All subjects across the 3 groups, regardless of their level of engagement with the Quitline, will be contacted by the study team at 10 weeks after study enrollment to assess their smoking status. For those reporting quitting smoking, they will be asked to complete the salivary cotinine measurement.

Table 1: Payment Structure									
	Connect to Way to Health	Quitline Enrollment	Quitline Counseling Calls			Submit Cotinine Swab*	Quit Confirmed ^		
Incentive, Quitline	\$15	\$15	\$15	\$15	\$15	\$15	\$15	\$20	\$25
Incentive, Smoking Cessation	\$15	\$15	0	0	0	0	0	\$20	\$100
No Incentive	\$15	0	0	0	0	0	0	\$20	0

\*For subjects that report quitting smoking (defined as no tobacco use in past 30 days) at the 10-week followup call. All subjects will receive \$20 for submitting the salivary cotinine swab, regardless of the result. ^Payment received for negative result, meaning cotinine level <30 ng per milliliter

#### Quitline Delivered Treatment

The PA Free quitline is funded by the Pennsylvania Department of Health and staffed by trained cessation counselors available 24 hours a day, 7 days a week, and most holidays. Counseling is available in English, Spanish, Arabic and can be provided in more than 15 additional languages through a third party. All cigarette or e-cigarette users who enroll in smoking cessation treatment will receive counseling and support consistent with accepted clinical practice guidelines. This treatment includes 5 proactive counseling calls, each designed to help develop problem-solving and coping skills, secure social support, and plan for long-term abstinence. Participants can also call an 800 telephone number as needed for additional support between proactive calls. The timing of counseling calls will be relapse sensitive and include a call 1 or 2 days after the quit date, another telephone call a week after the first call, and additional calls generally occurring at 1- to 2-week intervals thereafter. The call timing will be flexible and adjusted as needed. Completing the program involves completing at least of the 5 proactive counseling calls and reporting no tobacco use in the last 30 days.

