### 2 STUDY OBJECTIVES

The purpose of the study is to determine if financial incentives for adolescent smokers compared to no financial incentive increases engagement in a smoking cessation program.

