#### 2.1 Primary Objective (or Aim)

The primary objective of this study is to compare, through a pilot, randomized controlled trial, an incentive for Quitline engagement, an incentive for smoking cessation, or no financial incentive intervention on adolescent smoker enrollment and depth of engagement in a smoking cessation program (Free Smoker Quitline, hereafter referred to as the Quitline).

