### 2.2 Secondary Objectives (or Aim)

The secondary objective is to compare cotinine-confirmed 2-month quit rates across the 3 groups, among users who report abstinence at the 10-week follow-up call.

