### 3.1.3 Follow-up Phase

To be eligible for the follow-up phase, adolescents must self-report tobacco cessation. All study subjects will be contacted by the study team 10 weeks after study enrollment to inquire about smoking cessation (defined as no tobacco use in the last 30 days). For subjects that report quitting, to confirm cessation, subjects will complete a salivary cotinine specimen. The result will either be collected at the clinic or collected remotely, in the latter case performed in front of a live video-conference with a study staff member to confirm adherence. The result can be reported immediately.

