### 5.2 Efficacy Evaluations

The main outcome of interest is adolescent smoker completion of the smoking cessation program, defined as the proportion of smokers identified in the clinic that enroll, use, and complete the Quitline program compared across the 3 groups.

The secondary outcome is to confirm abstinence, via salivary cotinine concentration of <30 ng per milliliter at 10 weeks after study initiation.

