### **6** STATISTICAL CONSIDERATIONS

#### 6.1 Primary Endpoint

The main outcome of interest is adolescent cigarette or e-cigarette user completion of the smoking cessation program, defined as the proportion of smokers identified in the clinic that enroll, use, and complete the Quitline program compared across the 3 study arms.

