#### 6.3.2 Efficacy Analysis

We will calculate proportions for the clinical outcomes (enrollment, use, and completion of the Quitline program) and evaluate the magnitude and statistical significance of differences between the 3 groups. Intention-to-treat analysis will be used so that subjects will be analyzed according to the group to which they were initially randomized. Secondary analyses will describe results for participants as-treated. Categorical variables will be compared between groups using chi-square tests. Multivariable logistic regression models (that potentially include confounding variables) will be used to compare quit rate between groups. These models will include indicator variables for each of the financial incentive groups; the no financial incentive group will be the reference. The treatment groups will differ significantly from usual care if its indicator variable differs significantly from zero (p-value < 0.05 as criterion for statistical significance in a likelihood ratio or Wald's test). A Wald's test of the hypothesis that the two indicator variables are equal will also be performed (hypothesis that the probability of a subject quitting is the same for both financial incentive groups). We will explore for potential confounding by referral bonuses in the models and adjust if necessary.

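### The only definition of completing the Quitline program also requires a report of 30-day abstinence, so the primary outcome, applied as written, mixes engagement with quitting

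*Combined protocol and SAP*

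**What the plan says.** Section 2 sets the purpose as learning whether a financial incentive "compared to no financial incentive increases engagement in a smoking cessation program". The primary objective in 2.1 is the effect on "adolescent smoker enrollment and depth of engagement in a smoking cessation program". Quitting is handled separately: "The secondary objective is to compare cotinine-confirmed 2-month quit rates across the 3 groups" (2.2), with salivary cotinine below 30 ng/mL at 10 weeks as the endpoint (6.2).

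The primary outcome in 5.2 is "defined as the proportion of smokers identified in the clinic that enroll, use, and complete the Quitline program", and 6.1 repeats it. Neither section says what completing means. The only statement that does is the last sentence of Quitline Delivered Treatment in 7.1: "Completing the program involves completing at least of the 5 proactive counseling calls and reporting no tobacco use in the last 30 days". The number of calls is absent from the text supplied. It may have been lost when the PDF was read, and nothing here depends on it.

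Section 7.1 also has a calls-only concept, maintaining involvement (5 proactive calls, no abstinence condition), but it serves as a payment rule. The analysis section adds: "We will calculate proportions for the clinical outcomes (enrollment, use, and completion of the Quitline program".

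**The concern.** The completion sentence joins two conditions with "and": calls, and a report of no tobacco use. If it governs the primary outcome, an adolescent who takes every call but has not quit counts the same as one who never took a call. That departs from an objective about depth of engagement. It also places in the primary outcome the same 30-day criterion that opens the way to the secondary one, since at 10 weeks the study team contacts all subjects "to inquire about smoking cessation (defined as no tobacco use in the last 30 days") and only those reporting cessation give a cotinine sample.

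The mixing matters more here than in most trials because the incentive arms are built to reward different behaviors. Section 6.4 says the pilot is to supply effect sizes for a larger study. If the main effect size combines calls with quitting, it is a poor planning input for a trial of engagement.

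**Working it through.** **1. Is there another definition?** Enrolling is defined in 7.1 (connecting with a counselor, giving a smoking history, discussing the program). Maintaining involvement is defined in 7.1 for payment. Use is defined nowhere. Completing is defined only in the sentence quoted above. Sections 5.2, 6.1, 6.3.2 and the abstract use the word without defining it.

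**2. What separates the two incentive arms?** From 7.1 and Table 1, Quitline vs cessation arm:
- connecting to the platform: $15 vs $15
- enrollment: $15 vs $15
- calls: 5 x $15 = $75 vs $0
- swab: $20 vs $20
- confirmed quit: $25 vs $100

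The arms differ only on calls and confirmed quitting, which are the behaviors behind the two conditions of the completion sentence. Enrollment, which 6.3.2 reports separately, is paid identically in both.

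**3. How does the combination behave?** Let c be the proportion completing the required calls and a the proportion of those who report abstinence. Combined completion is c x a.
- If a is the same in both arms, the risk difference becomes a x (c1 - c2), and the risk ratio stays c1/c2.
- The order of the Quitline and cessation arms reverses only if a(cessation)/a(Quitline) exceeds c(Quitline)/c(cessation).

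**4. Illustration.** The plan states no rates and no power, so there is no figure of its own to reproduce beyond 3 x 20 = 60. All rates below are assumed.

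Quitline vs cessation, 20 per arm, exact binomial, calls 60% vs 35%. The reversal threshold is 0.60/0.35 = 1.71.

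| Abstinence among call-completers | Outcome compared | Difference (points) | Ratio | Quitline arm observed ahead |
|---|---|---|---|---|
| not required | 60% vs 35% | 25 | 1.71 | 93% |
| 25% vs 50% | 15% vs 17.5% | -2.5 | 0.86 | 33% |
| 50% vs 50% | 30% vs 17.5% | 12.5 | 1.71 | 78% |
| 50% vs 25% | 30% vs 8.75% | 21.25 | 3.43 | 94% |
| 80% vs 30% | 48% vs 10.5% | 37.5 | 4.57 | not computed |

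The difference can reverse, shrink or widen.

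For incentive against no incentive, take calls at 60% vs 20%. The difference is 40 points (12 vs 4 subjects). With 50% abstinence among call-completers in both arms it is 0.30 - 0.10 = 20 points (6 vs 2 subjects), and the ratio stays at 3. Approximate power at two-sided 0.05 falls from 75% to 35%. The normal approximation is rough at these counts.

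**The case against.** **The completion sentence describes the Quitline's own service, not the endpoint.** Sections 5.2 and 6.1 do not cite it, and it stands in the intervention section. This is fair: a reader might infer that the plan expressly adopts the combination as its primary endpoint, and it does not. But an analyst looking for the meaning of completing finds nothing else. If the sentence is not meant to apply, the primary outcome has no definition of completion.

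**Calls may be reported anyway.** A reader might conclude that no calls-only effect size will be produced. The documents do not support that. Use has no definition, and 7.1's maintaining involvement is a natural meaning for it, so 6.3.2 may cover calls. What stands is that nothing guarantees it.

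**The arms are not paid for wholly separate halves.** Correct. The Quitline arm is paid for calls and, less, for quitting; only the cessation arm is unpaid for calls. The point rests on where the payments differ.

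**Missing reports and late quitters.** It is tempting to add that a missing abstinence report has no scoring rule. On plain wording, a subject who makes no report has not met the condition. It is also tempting to cite a subject who takes every call but quits too late for 30 abstinent days by week 10, for example on day 45. That fits 7.1 poorly. If the 5 calls are those described there (1 or 2 days after quitting, a week later, then three more at 1- to 2-week intervals), the fifth falls between 1 + 7 + 21 = 29 and 2 + 7 + 42 = 51 days after quitting. For a day-45 quitter that is day 74 at the earliest, after week 10. Timing is flexible, so such a case is possible but not typical. The same schedule means the report could be made to the Quitline; the sentence does not tie it to the 10-week contact.

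**It is a pilot without a power calculation.** True, and this limits the consequence. But effect sizes are its stated product.

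**Conclusion.** The concern stands as a mismatch between a stated rule and the objective. The only definition of completing the program includes abstinence, while the objective is engagement and quitting has a separate endpoint. Taken alone, the combined outcome cannot show whether an incentive moved calls or quitting, and a separate calls-only estimate is not assured.

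The size and direction are unknown. A reader might infer from the illustration that the trial will understate or reverse the Quitline arm's advantage. The documents do not support this: every rate is assumed, results run in both directions, reversal under those assumptions needs an abstinence ratio above 1.71, and equal abstinence leaves the risk ratio unchanged.

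This should be fixed. Separate reporting of enrollment and use, and the availability of the call data, soften it.

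**What to change.** - In 6.1, and to match in 5.2, 7.1 and the abstract, define primary completion as taking a stated number of the 5 proactive calls, as recorded by the Quitline, irrespective of smoking status. Count calls the same way in all 3 arms, and score subjects who do not enroll as non-completers. The sponsor must supply the number.
- Define use, for example as at least 1 proactive call.
- Report the number of calls (0 to 5) by arm as the measure of depth.
- Leave abstinence to the secondary endpoint.
- Keep the combined definition as an additional outcome, with its call and abstinence components shown by arm.

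Sections 9.5 and 9.7 refer to subjects enrolled after AM13, so subjects may already be in the trial. The change should be a dated amendment, with its reason recorded, made without looking at outcomes by arm.

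No new data are needed: 7.1 has Quitline engagement reported to the platform in real time and all arms contacted at 10 weeks. The cost is an amendment and a main outcome that no longer matches the current combined definition, which reporting both covers.
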